12.0 Data Management

Sample size and power.

Our primary hypothesis is that use of a preoperative quadratus lumborum block will decrease opioid consumption, measured in intravenous (IV) morphine equivalents (ME), by 30%.

$H_0: ME_{QL} \neq ME_{no\ block}$

$H_A: ME_{QL} < ME_{no\ block}$

The primary analysis will be a one-sided test of mean IV ME opioid consumption. Preliminary data on IV ME opioid consumption in hip arthroscopy were reviewed. In people with no preoperative block, IV ME opioid consumption averaged 18.0 ± 3.2 ; people with preoperative block averaged 9.6 ± 8.7 .

Sample size was determined using G*Power version 3.1.9.2 software. Using preliminary data, we estimate that we will need 19 subjects in each group (N=38) to have sufficient power (80%) at $\alpha=0.05$ to test the hypothesis of a 30% decrease in IV ME opioid consumption in patients having a QL block vs. those with no block. Accounting for a possible 20% withdrawal, we anticipate the need to enroll 46 total subjects.

Baseline clinical and demographic factors for each group will be collected. Categorical data will be compared across the two groups with Chi-square tests of homogeneity and continuous data will be compared with t-tests for means. Covariables determined to be associated with IV ME opioid consumption will be assessed for inclusion in a multivariate linear model.

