6.0 Number of Subjects

46

*Sample size was determined using G*Power version 3.1.9.2 software. Using preliminary data, we estimate that we will need 19 subjects in each group (N=38) to have sufficient power (80%) at alpha=0.05 to test the hypothesis of a 30% decrease in IV ME opioid consumption in patients having a QL block vs. those with no block. Accounting for a possible 20% withdrawal, we anticipate the need to enroll 46 total subjects.*

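### Does the not-equal sign in the null hypothesis, with no sidedness beside alpha in the sample-size statement, undermine the primary test or its 80% power?

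*Combined protocol and SAP*

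**What the plan says.** Section 12.0 (Data Management, under the sample size and power subheading) sets the null as "H_0: ME_{QL} \neq ME_{no\ block" and the alternative as "H_A: ME_{QL} < ME_{no\ block". The primary hypothesis just above them is directional: the block "will decrease opioid consumption, measured in intravenous (IV) morphine equivalents (ME), by 30" percent. The line after the two hypotheses is "The primary analysis will be a one-sided test of mean IV ME opioid consumption".

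Preliminary means follow, and then the sample-size sentence: 19 per group (N=38) "to have sufficient power (80%) at $\alpha=0.05$ to test the hypothesis of a 30% decrease in IV ME opioid consumption". Section 6.0 (Number of Subjects) repeats that sentence. Neither copy states the sidedness of the 0.05, and Section 6.0 does not mention a one-sided test anywhere.

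**The concern.** A null and its alternative should not overlap, and the null should contain the boundary at which the type I error is controlled. Here the alternative (block lower than no block) lies inside the printed null (block different from no block), while equality lies outside it. Read literally, rejecting this null would mean concluding that the arms are equal, the reverse of the trial's aim. This is the only formal statement of hypotheses for the primary endpoint.

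The bare 0.05 adds to the unease. A reader of Section 6.0 alone could take it as two-sided, and the not-equal sign might seem to support that. If the primary analysis were then run two-sided at 0.05, the stated 80% power would not hold. If it is run one-sided at 0.05, the false-positive rate in the favourable direction is 5% rather than 2.5%, and Section 6.0 does not show this. At stake would be whether the decision rule is defined and whether the power claim is true of it.

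**Working it through.** **Which test is specified?** Three statements in Section 12.0 bear on this besides the null: the primary hypothesis (a decrease), the alternative (block less than no block) and the sentence naming a one-sided test of means. All three point the same way. The null that fits them is block ≥ no block. Writing it as equality would give the same test, because the critical value of a one-sided t-test is set at the boundary, where the means are equal. The printed symbol therefore does not enter the computation of the test statistic, its reference distribution or the p-value.

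**Does the stated sample size match that test?**

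Inputs, all from Section 12.0:
- No-block group: "In people with no preoperative block, IV ME opioid consumption averaged 18.0 ± 3.2".
- Block group: mean 9.6, ± 8.7.
- Target: a 30% decrease; alpha 0.05; power 80%; 19 per group.
- Assumptions: each ± is an SD (the document does not label it), and the two SDs are combined as a root mean square.

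Calculation:
- Difference = 0.30 × 18.0 = 5.4.
- Combined SD = √((3.2² + 8.7²)/2) = √((10.24 + 75.69)/2) = √42.965 = 6.555.
- Standardised effect d = 5.4/6.555 = 0.824.
- At n = 19 per group: noncentrality = d × √(n/2) = 0.824 × √9.5 = 2.54, with 2 × 19 − 2 = 36 degrees of freedom.

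Power of the two-sample t-test from the noncentral t distribution:

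| Per group | One-sided 0.05 | Two-sided 0.05 |
|---|---|---|
| 18 | 78.1% | 67.0% |
| 19 | 80.1% | 69.5% |
| 24 | 87.8% | 79.8% |
| 25 | 89.0% | 81.4% |

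The smallest group size reaching 80% is 19 one-sided, which is the plan's figure, and 25 two-sided.

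**Could 19 have come from another reading?** Smallest group size for 80% power at 0.05 under other inputs:

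| Difference | SD | One-sided | Two-sided |
|---|---|---|---|
| 5.4 | 3.2 | 6 | 7 |
| 5.4 | 5.95 (simple average) | 16 | 21 |
| 5.4 | 8.7 | 33 | 42 |
| 8.4 (observed, 18.0 − 9.6) | 3.2 | 3 | 4 |
| 8.4 | 5.95 | 7 | 9 |
| 8.4 | 6.555 | 9 | 11 |
| 8.4 | 8.7 | 14 | 18 |

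None of these gives 19. Of the combinations tried, only the 30% decrease with the combined SD and a one-sided 0.05 test does.

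**Do the unequal SDs matter?** Simulating Welch's test with SDs 3.2 and 8.7 at 19 per group gives about 79% power at one-sided 0.05 and about 68% at one-sided 0.025. The picture is the same.

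**The case for a change.** The strongest case for a change is that the statement is wrong on its face, concerns the primary endpoint, and would cost only a few words to correct. Other text also leaves some room for a two-sided reading. Section 1.0 describes the purpose as evaluating a difference, without direction. The last paragraph of Section 12.0 names t-tests and a linear model without sidedness. An analyst who defaulted to two-sided 0.05 would have about 70% power, roughly 10 points below the stated figure (80.1 − 69.5 = 10.6). An analyst who felt free to choose could settle the sidedness after seeing the data.

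Part of this stands. The printed null is wrong, unless the symbol was misread when the text was taken from the PDF, which cannot be checked here. Section 6.0 read alone does not tell the reader which error rate the 80% refers to.

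The rest does not carry over to the plan. The sidedness of the primary test is fixed in advance in words, between the hypotheses and the sample-size sentence and under the same subheading, so an analyst following Section 12.0 has no choice left open. The hypothesis in Section 1.0 is itself directional, and the t-tests in the closing paragraph belong to the comparison of baseline factors. The 10-point gap is a property of a different test and not a shortfall in this one. Preferring two-sided 0.05, or wanting a two-sided 95% interval and two-sided power reported alongside, is a view about convention. It does not follow from the error in the symbol.

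**Conclusion.** The concern does not call for a change. The not-equal sign is a clerical slip that the surrounding text resolves, and the missing word in the sample-size sentences is supplied by the declaration just before one of them. The planned one-sided test of means is valid, and its stated size and power reproduce: 19 per group, 80.1%. Correcting the symbol and repeating the word one-sided would leave the analysis, the p-value, the sample size and the conclusion as they are.

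This rests on reading the ± values as SDs and combining them to 6.555. Neither is stated, but both are supported by the exact match to 19. It also rests on the one-sided sentence in Section 12.0 governing the primary analysis. If the primary analysis were instead reported two-sided at 0.05, power at 19 per group would be 69.5% and 25 per group would be needed for 80%, but that would depart from the plan as written.

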4.0 Study Endpoints (if applicable)

- Our primary outcome is opioid consumption including intraoperative consumption exceeding 100µg of fentanyl and all postoperative opioid consumption in the postoperative anesthesia care unit (PACU).
- Secondary outcomes include visual analog pain scaled on PACU arrival and discharge, PACU duration, patient satisfaction, block duration and opioid related side effects.

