Care in the perioperative period will otherwise be standardized. As part of routine care, all patients will receive general anesthesia. After receiving 100µg of fentanyl intraoperatively, hydromorphone or morphine will be administered and titrated by the anesthesia care team for postoperative pain control. In the post-anesthesia care unit (PACU), hydromorphone or morphine would continue to be titrated by the PACU nurse for the patient's comfort. The total opioids administered after the initial 100µg of fentanyl would be compared between groups in order to evaluate the effect of the quadratus lumborum block.

Data collection will begin after informed consent is completed. Data collection will include demographic data, operative date/time, medications administered intraoperative and postoperative, time to meet discharge criteria in PACU and visual analog scores (VAS) for pain and satisfaction. VAS scores for pain will be collected prior to surgery, on PACU arrival (when aware enough to do so) and upon meeting PACU discharge criteria. Patient satisfaction will be recorded upon meeting PACU discharge criteria. Effects of the block (numbness or motor weakness) will be recorded. Opioid side effects including nausea, vomiting, and itching will also be noted. Patients will be called on postoperative day one to assess block duration and satisfaction with care.

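### The preoperative pain score is collected but never used in analysing the secondary PACU pain outcomes; a pre-specified baseline-adjusted analysis would cost almost nothing.

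*Combined protocol and SAP*

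**What the plan says.** Section 10.0 sets three pain assessments: "VAS scores for pain will be collected prior to surgery, on PACU arrival (when aware enough to do so) and upon meeting PACU discharge criteria". Section 4.0 gives the two PACU assessments secondary status: "Secondary outcomes include visual analog pain scaled on PACU arrival and discharge, PACU duration, patient satisfaction, block duration and opioid related side effects".

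Section 12.0 contains three statements on analysis:

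- For the primary outcome: "The primary analysis will be a one-sided test of mean IV ME opioid consumption".
- For other data, directly after the sentence "Baseline clinical and demographic factors for each group will be collected", it plans chi-square tests for categorical variables and says that "continuous data will be compared with t-tests for means".
- For adjustment: "Covariables determined to be associated with IV ME opioid consumption will be assessed for inclusion in a multivariate linear model".

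Section 12.0 does not mention pain, the VAS or any secondary outcome by name. No section gives a VAS standard deviation, a target difference in VAS, or a correlation between preoperative and PACU scores.

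**The concern.** The same scale is to be measured in the same patients before and after treatment, yet nothing in the plan connects the two measurements. The one linear model concerns opioid consumption. If the t-test sentence covers the PACU scores, they are compared without adjustment; if it does not, they have no stated analysis.

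Two things are at stake, both on a secondary outcome. The first is precision: with about 19 patients per arm the pain comparison will be wide, and a baseline on the same scale is usually the most obvious covariate for narrowing it. The second is pre-specification: with no model named, the choice between an adjusted and an unadjusted pain result could be made after both have been seen.

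**Working it through.** **The plan's own figure.** Inputs from 12.0: control mean 18.0, SDs 3.2 and 8.7 (reading the ± figures as SDs), a 30% decrease, one-sided alpha 0.05, power 80%.

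- Difference: 0.30 × 18.0 = 5.4. Pooled SD: √((3.2² + 8.7²)/2) = 6.555. Standardized difference: 5.4/6.555 = 0.824.
- n per arm = 2 × (1.645 + 0.842)² / 0.824² = 18.2, so 19. Exact power with the noncentral t is 80.1%. The stated 19 per arm (N = 38) reproduces.

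That figure is for opioid consumption. The plan makes no power claim for pain, so N = 38 is used below only as the planned analysis size.

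**Gain from baseline adjustment.** Let ρ be the correlation between preoperative and PACU VAS. It is assumed over a range because the documents do not give it. Relative to an unadjusted comparison of the PACU score, the variance of the adjusted difference is

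(1 − ρ²) × (1 + 1/(N − 4)), where 1 + 1/(38 − 4) = 1.029.

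The second factor is the average small-sample price of estimating the slope. The CI width ratio is the square root of the product, and the equivalent unadjusted size per arm is 19 divided by the product. The power column takes an effect for which a two-sided t-test at 19 per arm has 80% power (0.93 SD) and gives the ANCOVA power with 35 instead of 36 degrees of freedom.

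| Assumed ρ | 1 − ρ² | × 1.029 | CI width | Equivalent n per arm | Power |
|---|---|---|---|---|---|
| 0 | 1.00 | 1.029 | about +1% | 18.5 | 78.8% |
| 0.2 | 0.96 | 0.988 | about −1% | 19.2 | 80.4% |
| 0.3 | 0.91 | 0.937 | about −3% | 20.3 | 82.4% |
| 0.5 | 0.75 | 0.772 | about −12% | 24.6 | 89.0% |
| 0.6 | 0.64 | 0.659 | about −19% | 28.8 | 93.2% |

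Break-even: (1 − ρ²) × 1.029 = 1 gives ρ² = 1 − 1/1.029 = 0.028, so ρ is about 0.17.

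**Chance imbalance.** In SD units, the standard error of the between-arm difference in preoperative VAS is √(2/19) = 0.32. By the normal approximation, about 12% of such trials would have an imbalance above 0.5 SD. At ρ = 0.5, an imbalance of 0.5 SD shifts the unadjusted pain difference by 0.5 × 0.5 = 0.25 SD.

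**Is the preoperative score a usable baseline?** Section 10.0 starts data collection once consent is complete. Sedation and the block or sham procedure also follow consent, in the holding area and before surgery. A score collected merely before surgery could therefore come after the block. Such a score could be affected by treatment and should not be used as a covariate.

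**The case against.** A reader might infer that the plan prescribes a t-test for PACU pain and so discards a known amount of precision. The documents support neither part. The t-test clause follows a sentence about baseline factors and may be limited to them; it never names the VAS. The loss also depends on a correlation that nobody has stated. Low values are plausible: the baseline is pain before the operation, whereas the outcome follows general anesthesia and opioids titrated during surgery and in the PACU. Titration to comfort tends to pull scores together, so the gain may be smallest at discharge. Below about 0.17, adjustment slightly widens the interval, and at 0.3 the benefit is only about 3%.

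Nor does possible chance imbalance make the unadjusted comparison invalid. It is unbiased under randomization, and its standard error already allows for such imbalance.

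These points stand and limit the size of the concern. They do not remove it. On either reading of the t-test sentence the baseline goes unused, and one added sentence repairs both. The possible loss is about one percentage point of power, whereas the possible gain is several times that from a moderate correlation upward.

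Two practical objections also stand. A change to 12.0 alone is not enough, because the timing of the baseline score in 10.0 has to be settled. And arrival scores depend on the patient being aware enough to give them, so some may be missing; adjustment for baseline does not by itself solve that.

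**Conclusion.** The point holds as one of efficiency and pre-specification on secondary outcomes. The plan collects a preoperative pain VAS and does not use it in analysing PACU pain, for which it states either an unadjusted t-test or no method at all. An unadjusted comparison would be valid but probably less precise.

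The benefit ranges from nil or slightly negative at correlations below about 0.17 to a 12% to 19% narrower interval at 0.5 to 0.6. This rests on an assumed correlation, 38 patients with both scores, a roughly linear relation between them, and a preoperative score taken before any study procedure. The primary analysis and the 19 per arm are untouched. The change is worth making because it costs so little, not because the present plan would give a wrong answer.

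**What to change.** In 12.0, state that PACU-arrival VAS, and likewise the VAS at discharge criteria, is analysed by ANCOVA with arm and preoperative VAS as the only terms, reporting the adjusted mean difference with a 95% CI. State also that the number of patients without an arrival score is reported by arm. In the same place, say whether the chi-square and t-test sentence is meant for baseline factors only. A change-from-baseline score is not a substitute: its variance relative to the raw score is 2(1 − ρ), which is 1.4 at ρ = 0.3 and falls below 1 only when ρ exceeds 0.5.

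In 10.0, state that the preoperative VAS is recorded after consent and before sedation and the block or sham procedure.

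Cost: a few sentences across the two sections and one degree of freedom in the pain analysis, with about one percentage point of power lost if the correlation is near zero. No additional patients or assessments are needed.

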13.0 Provisions to Monitor the Data to Ensure the Safety of Subjects

Any adverse events related to placement of nerve blocks will be treated according to MUSC Hospital policy and procedures and the practice of the Department of Anesthesia.

The Department of Anesthesia's DSMB will review the study on an annual basis. Any adverse events will be reported in real time and reviewed by the DSMB. Adverse events will be reported to MUSC's IRB per policy.

All data will be kept in a locked office, in a locked cabinet, and electronic data will be stored on a password protected MUSC server. Only CITI certified, IRB approved study team members will have access to data.

14.0 Withdrawal of Subjects

- Subjects may withdrawal from the study at any time.

15.0 Risks to Subjects

- Risks of anterior approach to the quadratus lumborum block are similar to most truncal blocks and include infection, bleeding, local anesthetic systemic toxicity (LAST) and nerve damage. These risks are all less than 1%. Infection risk is minimized by utilizing appropriate antiseptic and sterile

technique as is standard for any regional procedure. Risk of a retroperitoneal hematoma (bleeding) is increased with the posterior approach to the quadratus lumborum block because of its transmuscular approach and likelihood of abdominal branches of lumbar arteries in the path of the needle. For this reason, the posterior approach to the quadratus lumborum block will not be used for this study. The risk of LAST is a risk with any regional procedure and is minimized by frequent aspiration, incremental local anesthetic injection and vital signs monitoring throughout.

- There is also a risk of loss of confidentiality.
- Any puncture of the skin (including the saline skin wheel for the no block group) poses a risk of infection. Prepping the skin with chlorhexidine prior to skin puncture lowers this risk to less than 1%.

